## **Section F: Design/Procedure**

### **F1. Design**

Select one category that most adequately describes your research:

c) Pilot

Discuss the research design including but not limited to such issues as: probability of group assignment, potential for subject to be randomized to placebo group, use of control subjects, etc.

The clinical trial will compare the effectiveness of iCBT to standard CBT (sCBT) and treatment as usual (TAU). A total of 252 Veterans from all war eras will be recruited who have at least one of the following disorders: PTSD, panic disorder (PD), social anxiety disorder (SAD) and generalized anxiety disorder (GAD). Veterans with or without co-occurring depression will be included. Participants will be randomized to iCBT, sCBT, or TAU. The study design uses unequal randomization to the active intervention arms and to treatment as usual to reduce unnecessary recruitment. Thus, the percent chance that participants will be randomized to one of the three conditions are: 37% iCBT, 37% sCBT, and 24%TAU. Participants in iCBT will receive treatment over one weekend (16 total session hours); those in sCBT will receive the same treatment weekly, over 12 weeks (16 total session hours); and those assigned to TAU will receive routine clinical care. Assessments will be completed at four time points: baseline, 1-month, 3-months, and 6-months.

This protocol should be considered minimal risk because the likelihood and degree of discomfort anticipated in this intervention are lower than what people would encounter in daily life. This is a non-invasive behavioral intervention that is designed as a two-day workshop to teach participants about anxiety and provide them with opportunities to practice examining and adjusting their thoughts based on evidence. Participants have the benefit of having trained therapists available to guide and help them engage in these exercises. The workshop is similar to other classes and seminars people may attend in daily life. The room is set up as a classroom with individual desks and chairs for participants. Breaks are scheduled throughout the day, and participants are informed that they may take a break whenever they need.

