## Assessment Battery

The assessment battery will consist of the following: (1) Community Reintegration of Injured Service members – Computer-Adaptive Test (CRIS-CAT), a commonly used measure of community reintegration following deployment; (2) Short-Form 12 Health Survey (SF-12), measures eight domains related to physical and mental health, health perceptions, and the impact of physical or emotional problems on general functioning via self-report; (3) Beck Anxiety Inventory (BAI) assesses the severity of anxiety symptoms, minimizing those that overlap with depression; (4) Beck Depression Inventory - Second Edition (BDI-II) assesses severity of depressive symptoms; (5) Quality of Life Enjoyment and Satisfaction Questionnaire- Short Form (Q-LES-Q-SF) is a brief, 16-item measure of subjective functioning and satisfaction across a range of life domains including work, leisure activities, social relationships, and physical health; (6) Saint Louis University Mental Status Exam (SLUMS) is an 11-item clinician-administered screening measure of cognitive impairment; (7) Anxiety Disorders Interview Schedule DSM-5 (ADIS-5) is a gold-standard semi-structured clinician interview used to assess for the presence of all anxiety disorders including PTSD. Modules examining the presence of psychosis, mood and

substance abuse disorders are also included; (8) Demographic and Military Survey is a brief questionnaire we have used in previous studies that inquires about general demographic and military information. Veterans are asked about their periods of service, deployment dates, whether they seek healthcare outside of VA, and other information pertaining to their education and employment history; (9) Perceived Barriers to Seeking Mental Health Services (PB-SMHS) assesses concerns specific to Veterans that are related to seeking mental health counseling and related services; and (10) Client Satisfaction Questionnaire-8 (CSQ-8) is a brief 8-item measure used to assess overall treatment satisfaction. All measures will be administered at each assessment period, except the ADIS-5, Q-LES-Q-SF, SLUMS, Demographic Questionnaire, and PB-SMHS, which will only be administered at baseline. The CSQ will only be administered at 1-month and 3-month follow-up periods. The complete battery of assessments can be administered in 2-3 hours.

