### **G2. Data Analysis**

Provide a description of your plan for data analysis. State the types of comparisons you plan (e.g. comparison of means, comparison of proportions, regressions, analysis of variance). Which is the PRIMARY comparison/analysis? How will the analyses proposed relate to the primary purposes of your study?

For our primary analyses, we will compare changes between the iCBT, sCBT, and TAU groups at all time periods in a single regression using a hierarchical mixed-model analysis. Because the number of patients randomized to the 3 groups is not equal, we will test for unequal variances and if necessary, will account for this in our regression models. For outcomes with unequal variances, in the mixed model, we will estimate the variances separately and adjust the degrees of freedom for the unequal variances. A priori covariates will also be included in the model. A significant time-by-treatment interaction will be followed by pairwise contrasts to determine whether the active interventions differed from TAU and whether the active treatments differed from each other. We will report the p-values and adjust p-values post-hoc using multiple comparisons procedures (e.g., Bonferroni) as recommended in the literature. For secondary analyses, we will run hierarchical linear regression models for each outcome using the baseline and 1 month data and with the a priori covariates. Hierarchical logistic regression models will be used to test differences in treatment engagement across conditions.

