Statistical Methods

Specific Aim 1: Examine the effectiveness of iCBT in improving community reintegration and overall quality of life. Community reintegration will be measured using the 3 subscales of the CRIS-CAT: extent of participation, perceived limitations, and satisfaction with participation. Quality of life will be measured by the SF-12 Physical Component Summary (PCS) and Mental Component Summary (MCS) scores. Although our quantitative analyses will be intention-to-treat, we will provide information on the number of and characteristics of any participants who did not receive the treatment as allocated or who did not complete the study. We will tabulate baseline characteristics, such as age, race, gender, disease severity, comorbidities, and psychotropic medications. Based on recommendations of the CONSORT group,⁸¹ we will adjust analyses for variables we have decided *a priori* may be important to control (i.e., depression, period of service [OEF/OIF/OND, Gulf War, and other] concomitant psychotropic medication use, and the primary diagnosis stratification variable). Results from both an intent-to-treat and treatment completer analyses will be compared.

Hypothesis 1a: *iCBT and sCBT will significantly improve community reintegration and quality of life relative to TAU at 3-and 6-month follow-ups.* To compare changes between the iCBT, sCBT, and TAU groups at all time periods in a single regression, we will use a hierarchical mixed-model analysis. Because the number of patients randomized to the 3 groups is not equal, we will test for unequal variances and if necessary, will account for this in our regression models. For outcomes with unequal variances, in the mixed model, we will estimate the variances separately and adjust the degrees of freedom for the unequal variances. The model will contain terms for the intercept, treatment, time period and interaction between time and treatment. *A priori* covariates as well as the stratification variable of anxiety disorders will also be included in the model. A significant time-by-treatment interaction will be followed by pairwise contrasts to determine whether the active interventions differed from TAU and whether the active treatments differed from each other. We will report the p-values and adjust p-values post-hoc using multiple comparisons procedures (e.g., Bonferroni) as recommended in the literature.⁸²

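### As most naturally read, the H1a/H2a mixed model leaves its time-by-treatment test essentially unadjusted for the named covariates; covariate-by-time terms would deliver the promised adjustment

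*SAP*

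**What the plan says.** Under Specific Aim 1 the SAP commits to adjusting for variables chosen in advance: "depression, period of service [OEF/OIF/OND, Gulf War, and other] concomitant psychotropic medication use, and the primary diagnosis stratification variable". For Hypothesis 1a it gives the purpose of the model as "To compare changes between the iCBT, sCBT, and TAU groups at all time periods in a single regression" and lists the terms: "The model will contain terms for the intercept, treatment, time period and interaction between time and treatment". It adds that the a priori "covariates as well as the stratification variable of anxiety disorders will also be included in the model". Protocol G2 makes this the primary analysis and says only: "A priori covariates will also be included in the model". No covariate-by-time term appears in either document, and the baseline outcome is not listed as a covariate for H1a.

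Inference starts from the interaction: "A significant time-by-treatment interaction will be followed by pairwise contrasts". The SAP repeats the analysis for Hypothesis 2a with the BAI and BDI-II. Protocol F1 sets the visits: "Assessments will be completed at four time points: baseline, 1-month, 3-months, and 6-months".

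Hypothesis 1b differs. Its model takes the 1-month value as outcome and the baseline value as a covariate, so there the same covariates do adjust the treatment effect.

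**The concern.** The SAP wants its treatment comparisons adjusted for factors thought to matter, including the factor used to stratify. The quantity tested for H1a and H2a is a difference in change over time. A patient-level covariate with one coefficient for all visits moves that patient's baseline and follow-up values by the same amount, so it has no effect on change.

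A report that followed the SAP would call its primary test adjusted when the interaction estimate is not. If the arms differed by chance in a factor that predicts improvement, the test would carry that imbalance uncorrected. Any precision those factors could give to the change contrast would also be lost.

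**Working it through.** **1. The plan's own figure.** Protocol G1 states 80% power for an effect of 0.57 with 49 per group in a two-group t-test, two-sided α = 0.05.
- n = 2(1.960 + 0.842)²/0.57² = 48.3, so 49 per group (49.3 by the t distribution).
- Power at 49 is 80.5% (normal) or 79.8% (t).
- 95 × 0.8 = 76, and 76/49 gives an implied design effect of 1.55.

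The figure reproduces. It assumes no gain from covariates.

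**2. Algebra.** Let μ(g,t) be the mean of arm g at visit t, and x the baseline covariates with a single coefficient vector γ. Arm-by-visit is saturated, so in complete data the fitted mean is

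μ̂(g,t) = ȳ(g,t) − x̄(g)′γ̂.

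The fitted change is μ̂(g,t) − μ̂(g,0) = ȳ(g,t) − ȳ(g,0). The covariate term drops out whatever γ̂ is. A therapist random intercept also shifts all visits equally and cancels.

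With visit-specific coefficients γ(t), the difference in change between arms g and h gains the term −[x̄(g) − x̄(h)]′[γ̂(t) − γ̂(0)]. This is the correction for imbalance in factors that predict change.

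**3. Numerical check.** Three arms (95/95/62) and four visits, fitted by maximum likelihood under compound-symmetry (CS) and unstructured (UN) covariance, with 60 simulated trials per setting. Covariate effects, covariances and dropout patterns are assumptions. The contrast is iCBT versus TAU at 3 months, in SD units, except for the time-varying row, where only UN was run. The table shows how far it moves when main-effect covariates are added to a model with none.

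| Setting | Mean shift | Largest shift |
|---|---|---|
| Change, complete data | 0 | below 4×10⁻¹⁵ |
| Change, 20% random dropout, direct fit | 0.010–0.013 | 0.04 |
| Change, dropout related to depression and arm, direct fit | 0.04–0.05 | 0.10 |
| Level at 3 months, complete data | 0.07 | 0.21 |
| Change, time-varying covariate, complete data | 0.02 | 0.08 |

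- Change contrast, complete data: the SE is the same with and without main effects (0.187 CS, 0.194 UN).
- Therapist random intercept with unbalanced therapists, complete data: the largest shift was again about 4×10⁻¹⁵.
- Dropout related to depression and arm: the mean estimate was 0.60–0.61 without covariates and 0.55–0.56 with main effects, against a true value of 0.50.
- Level contrast: the SE fell from 0.200 to 0.180 (CS) or from 0.212 to 0.187 (UN).

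**4. Effect of covariate-by-time terms, complete data.** In the same simulations the change contrast moved by 0.04–0.05 SD on average (largest about 0.20). Its SE fell from 0.187 to 0.184 (CS) or from 0.194 to 0.187 (UN).

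A separate simulation (76/76/50, correlation 0.5, UN) varied the share of the variance of change that the covariates explain:
- 0%: SE +1%.
- 10%: SE −4%. Check: √0.90 = 0.949, times 1.01 = 0.958.
- 18%: SE −9%. Check: √0.82 = 0.906, times 1.01 = 0.915.

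An SE 4% smaller is worth 1/0.96² = 1.085, about 8% more patients (roughly 20 of 252). An SE 9% smaller is worth 1/0.91² = 1.21, about 20%.

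Carried to the G1 setting for illustration only (n = 49, d = 0.57, ignoring the df cost), power would be 79.8% at R² = 0, 83.7% at 10% and 87.8% at 20%.

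**5. Cost in parameters.** Taking four diagnoses (3 terms), three service periods (2), depression (1) and medication (1) gives 7 terms. Over three follow-up visits, 7 × 3 = 21 df.

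**The case against.** The strongest reply is that main effects only is inferred from silence: the documents say that the covariates are included, not how. That is correct. But the SAP lists the terms of the model and names one interaction, so main effects is the natural reading. If covariate-by-time terms were meant, the SAP needs to say so.

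A reader might infer that the covariates do nothing at all. The documents do not support that, for four reasons.

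- **Imputation and incomplete data.** The SAP's missing-data section puts all analysis variables into the imputation model, so naming the covariates can change the imputed values. It also plans analyses of observed data, and in direct fits to incomplete data main effects do move the estimate.
- **Contrast scale.** The SAP does not say whether the pairwise contrasts compare change or level. Level contrasts at 3 or 6 months would be adjusted. The interaction test that precedes them still would not be.
- **Response.** If the response were change scores, arm contrasts at each follow-up visit would be adjusted. By the same cancellation, the time-by-treatment interaction would not.
- **Timing of covariates.** The H1a text does not fix depression or medication at baseline, and the BDI-II is repeated: "All measures will be administered at each assessment period", with exceptions that do not include it. Time-varying values would change the interaction estimate, but treatment could affect them, and the BDI-II is itself an H2a outcome.

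It is also fair to say that randomisation keeps the test valid, that the sample size claims no covariate gain, and that the precision figures rest on an assumed R². All of this stands, and it limits the point to a cheap improvement.

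**Conclusion.** The point holds in a limited form. With baseline in the response, covariates fixed at baseline and one coefficient per covariate, the H1a and H2a time-by-treatment estimate is exactly the same with and without the covariates in complete data and in each imputed dataset. The adjustment that the SAP promises therefore reaches the interaction test only indirectly, through the imputation model or through direct fits to incomplete data.

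In simulation, covariate-by-time terms moved the 3-month contrast by 0.04–0.05 SD on average, and the SE effect ran from about +1% to −9%. Both depend on assumed covariate effects. A reader might conclude that the primary test is invalid or the trial underpowered for this reason. Neither follows: the unadjusted test is valid under randomisation, and the stated power is for an unadjusted t-test.

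**What to change.** In the SAP text for H1a, carried to H2a:

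- Add covariate-by-time terms for primary diagnosis and each a priori covariate.
- State that all covariates are fixed at their baseline values.
- State that the pairwise contrasts are differences in change from baseline at 3 and 6 months.

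An alternative is to model follow-up visits only, with the baseline value of the outcome by visit as well as the covariates by visit. Baseline must be included. Without it the model estimates a level difference. In simulation (76 versus 50 patients, complete data, 1,500 trials per setting, covariate effects assumed) that estimate differed from the change estimate by 0.15 SD on average. The SEs were alike at a residual correlation of 0.5, but at 0.7 they were 0.190 against 0.147, about 29% larger.

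If the depression covariate is the baseline BDI-II score, use the follow-up-only form for the BDI-II outcome, because the covariate would otherwise equal the baseline response.

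The change needs a few lines of text and no new data. It uses about 21 df, and the SE would be about 1% larger if the covariates turn out not to predict change.

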**Intensive Cognitive Behavioral Treatment:** The iCBT condition will contain the same treatment components as sCBT, but the intervention will be delivered over one weekend, lasting 8 hours each day (see weekend itinerary in Section S: file named "H42354 Study Measures"). A maximum of 6 Veterans may be enrolled per group cycle. Veterans will be asked to complete practice assignments using thought records during the treatment. They will also be asked to monitor and record their anxiety and mood outside of treatment.

**Treatment As Usual:** The TAU condition consists of routine clinical care patients would typically receive at the MEDVAMC. This may include medication management alone (visits once every 4 months, on average) or in conjunction with other forms of individual or group therapies that involve supportive counseling or educational and skills-based classes (e.g., anger management, PTSD Recovery 101, etc.). These time-limited classes typically occur once per week for a total of 8 – 12 weeks. The TAU condition may also include Veterans who participate in disorder-specific evidence-based interventions such as cognitive-processing therapy or prolonged exposure therapy, as these treatments reflect the current standard of routine care in VA. Information on participants' engagement in these and all other forms of mental health treatment during the study will be collected via self-report and chart review. This information will be examined and if needed, will be controlled for in subsequent analyses. Upon completing the 6-month follow-up, patients in this condition will be offered iCBT or sCBT.

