## **Section G: Sample Size/Data Analysis**

### **G1. Sample Size**

How many subjects (or specimens, or charts) will be used in this study?

Local: 335      Worldwide: 335

Please indicate why you chose the sample size proposed:

A total of 335 participants will be recruited for this study: 252 Veterans will be recruited to participate in the RCT; 40 Veterans who participated in iCBT and their family members (up to 40) will be invited to participate in the qualitative interview.

For the RCT, a total of 252 patients will be randomized across the 3 arms (95 to iCBT, 95 to sCBT, and 62 to TAU) to have 80% power to detect differences among groups in the primary outcomes. A recent meta-analysis of transdiagnostic treatment for anxiety demonstrated a medium effect size ( $g=.69$ ) on quality of life outcomes. Based on these findings, we are using a more conservative effect size of 0.50 to calculate the sample size that will need to be recruited and randomized to draw conclusions. We will use unequal randomization to the active intervention arms and to treatment as usual to reduce unnecessary recruitment. We also inflated the sample size to account for intraclass correlations among patients and for attrition and loss to follow-up in order to obtain the number that must be recruited for the study. The recruited sample size of 95 for iCBT and 95 for sCBT, assuming 20% attrition at 1 month and accounting for clustering of patients within therapists, will result in 49 patients per group for analysis. For our primary analyses, this sample size will have 80% power to detect a medium effect size of .57 using a two-group t-test with  $\alpha=.05$  two-sided significance level.

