Hypothesis 1b: *iCBT will result in improved reintegration/quality of life measures relative to sCBT at 1-month follow-up.* Only patients in the iCBT and sCBT groups will be used in the analyses. For each outcome, we will run a hierarchical linear regression model using the baseline and 1 month data and with the *a priori* covariates and anxiety disorder stratification variables. Patients will be nested within therapist. The models will contain the 1 month value as the outcome variable and the baseline value of the outcome as an additional covariate. A significant value for the parameter estimate for the intervention will indicate that the iCBT and sCBT groups differed at 1 month.

Specific Aim 2: Examine the effectiveness of iCBT in reducing anxiety/depression symptoms relative to sCBT and TAU. **Hypothesis 2a:** *iCBT and sCBT will significantly reduce anxiety and depression symptoms relative to TAU at 3-and 6- month follow-ups.* The analyses described for hypothesis 1a will be repeated for this hypothesis using the secondary outcomes. Anxiety will be measured using the BAI and depression measured using the BDI-II. **Hypothesis 2b:** *iCBT will result in improved anxiety/depression measures relative to sCBT at 1-month follow-up.* The analyses described for hypothesis 1b will be repeated for this hypothesis using the secondary outcomes.

Specific Aim 3 (Exploratory): Hypothesis 3a: *Compare rates of psychotherapy engagement in iCBT relative to sCBT.* We will use hierarchical logistic regression models to test if the iCBT and sCBT groups differed on treatment engagement (defined as the percentage of randomized patients who participated in 12 or more treatment hours). The outcome will be whether or not

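### The H1a/H2a model specifies no therapist or group clustering, although G1, H1b and H3a do; if it is left out, or added only as a constant intercept, the active-versus-TAU standard errors will be too small

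*SAP*

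**What the plan says.** Protocol G1 randomises 252 Veterans, "95 to iCBT, 95 to sCBT, and 62 to TAU". It says of the calculation: "We also inflated the sample size to account for intraclass correlations among patients and for attrition and loss to follow-up". For the two active arms, "assuming 20% attrition at 1 month and accounting for clustering of patients within therapists, will result in 49 patients per group for analysis". It gives neither the ICC nor the cluster size.

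The SAP's text for H1b states: "Patients will be nested within therapist". H2b repeats H1b, and H3a has its own sentence on therapist nesting.

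H1a compares changes across all three arms and all visits in one hierarchical mixed model: "The model will contain terms for the intercept, treatment, time period and interaction between time and treatment". It adds the a priori covariates and the diagnosis stratification variable. A significant time-by-treatment interaction leads to pairwise contrasts with adjusted p-values, Bonferroni being the example given. H2a repeats this for the BAI and BDI-II. Protocol G2 describes the same model as primary and adds no cluster term.

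On delivery, the Treatments part of Protocol F2 describes groups of at most 6 Veterans in both active arms, and a masters-level and a doctoral-level interventionist trained for both. There is no study therapist or study group in the third arm: "The TAU condition consists of routine clinical care patients would typically receive at the MEDVAMC".

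**The concern.** H1a and H2a carry the trial's claims that CBT beats usual care at 3 and 6 months. Patients who share a therapist or a treatment group are expected to have correlated outcomes, and G1 accepts this. A model that treats them as independent gives intervals that are too narrow and p-values that are too small for those claims.

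Two features make this more than a missing detail that an analyst would fill in correctly by habit. First, the cluster effect arises once treatment starts, so a cluster term constant over visits does not capture it in a contrast of changes from baseline. Second, TAU patients belong to no study cluster. The design is partially nested, and neither document says how TAU patients would enter a therapist-nested model.

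**Working it through.** **Inputs from Protocol G1.** Randomised 95/95/62; 20% attrition; 49 per active arm after clustering; detectable effect 0.57; two-sided 5%.

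**Assumptions.** The 1-month attrition figure is applied to TAU as well and carried to the H1a visits. The analysed change has unit SD, which a baseline/follow-up correlation of 0.5 gives. Clustering exists only in the active arms. Normal approximation throughout.

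**1. The plan's own figure.** Two groups of 49, effect 0.57: SE = √(2/49) = 0.2020, and power = Φ(0.57/0.2020 − 1.96) = 80.5%. The stated 80% is reproduced (79.8% with the t distribution).

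**2. Implied design effect.** 95 × 0.8 = 76, and 76/49 = 1.551. From 1 + (m − 1) × ICC, this is ICC 0.110 at m = 6 (a full group), or 0.015 at m = 38 (two therapists sharing an arm). Both values of m are assumptions.

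**3. One active arm versus TAU.** TAU retained: 62 × 0.8 = 49.6.
- SE without clustering: √(1/76 + 1/49.6) = 0.1825
- SE with clustering: √(1.551/76 + 1/49.6) = 0.2014
- Ratio 1.103, so the unclustered SE is 1 − 1/1.103 = 9% too small
- False positives at 5%: 2 × [1 − Φ(1.960/1.103)] = 7.6%
- False positives at a Bonferroni 1.67%: 2 × [1 − Φ(2.394/1.103)] = 3.0%

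**4. Sensitivity to the design effect.**

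| Design effect | SE ratio | False positives at 5% |
|---|---|---|
| 1.10 | 1.020 | 5.5% |
| 1.25 | 1.048 | 6.2% |
| 1.55 (G1) | 1.103 | 7.6% |

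At m = 6, the first two rows correspond to ICC 0.02 and 0.05. A simulated unclustered t-test (13 groups of 6 versus 50 TAU) gave 4.9% at ICC 0 and 7.4% at ICC 0.11.

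**5. The planned sequence.** I simulated a one-visit, 2-df interaction test followed by Bonferroni over three contrasts, at design effect 1.55 with cluster effects separate by arm.

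| | No clustering | Design effect 1.55, ignored |
|---|---|---|
| Interaction gate | 5.0% | 10.8% |
| Each active-versus-TAU contrast | 1.6% | 2.9% |
| Any of the three contrasts | 4.2% | 9.4% |

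**6. Why a constant intercept does not help.** Write a patient's value at visit t in cluster j as the mean plus u_j plus error. The change from baseline contains u_j − u_j = 0, so the term drops out of every difference in change. Calculating the SE directly for 15 clusters of 5 per active arm and 50 TAU, with a post-baseline cluster variance of 0.145, gives a true SE of 0.203. The model SE is 0.183 with no cluster term, and a constant intercept does not raise it. A post-baseline effect in the active arms only gives 0.203.

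**7. Power for active versus TAU.** With the design effect in the active arm only, Φ(0.57/0.2014 − 1.96) = 80.8%.

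**The case against.** The strongest reply is that the omission is read from silence. H1a is called hierarchical, a word the SAP also uses for the therapist-nested models. The quoted sentence lists fixed terms and states no random part at all, not even the within-patient correlation that any repeated-measures model needs. This stands: a reader might infer that H1a excludes clustering, and the documents do not support that. They leave it unspecified. But H1b and H3a are also called hierarchical and still get an explicit nesting sentence, and in H1a the word may mean only visits within patients.

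Nor does H1a define its response. If change scores are modelled, or if the contrasts are between-arm differences at a visit, a therapist intercept does not cancel. That is also fair, so the finding on the constant intercept is conditional. It applies to the natural reading, in which baseline is one of the visits and the time-by-treatment interaction is tested. The provision for unequal variances does not fill the gap, because clustering is covariance between patients.

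A reader might also infer that the trial's power is overstated. It is not: 49.6 retained in TAU already matches the effective 49 per active arm, and step 7 meets the stated 80% at 0.57.

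Finally, the gate and Bonferroni limit the error. Each active-versus-TAU contrast stays below 5%, at 2.9%, and the rate for either of the two is 5.4%. Step 5 shows, however, that they do not restore the rates that the procedure would otherwise have.

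**Conclusion.** The point holds as a specification gap with a known direction of error. If H1a and H2a omit clustering, or include it only as an intercept constant over visits with contrasts of change from baseline, the active-versus-TAU standard errors are too small whenever post-treatment outcomes are positively correlated within clusters.

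At G1's own implied design effect the shortfall is about 9%. That gives about 7.6% false positives for an unadjusted 5% test, about 3.0% for a contrast at 1.67%, and about 10.8% at the interaction gate. The gate figure assumes cluster effects separate by arm. If the same therapists treat in both arms, their main effect cancels between iCBT and sCBT but not against TAU.

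The size rests on an ICC and a cluster size that the documents do not give, and with weak clustering it is slight. G1's power statement needs no change. This should be settled in the SAP before analysis.

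**What to change.** In the SAP, state the random structure of the H1a/H2a mixed model:

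- Add a random treatment-cluster effect that acts at post-baseline visits (cluster-by-post-baseline or cluster-by-visit), not a constant intercept.
- Let it exist only in iCBT and sCBT. Each TAU patient is his or her own cluster, as is each active-arm patient who never starts treatment and has no assigned cluster.
- Use Kenward-Roger or Satterthwaite degrees of freedom.
- If only two interventionists deliver treatment, use the group cycle (up to 6 Veterans, so about 95/6 ≈ 16 per arm) as the cluster unit, because therapist has too few levels for a random effect.
- Keep the imputation model compatible with this structure. The SAP's PROC MI plan mentions no clusters, and imputing without them may dilute the correlation that the analysis model is meant to capture.

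The cost is slightly wider confidence intervals and some extra analysis and imputation work. No further patients or visits are needed, and cluster membership of treated patients is known from delivery.
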